## **ETHICS COMMITTEE CONCERNS**

1. Are the risks to the subjects minimised by using procedures which are consistent with sound research design and which do not unnecessarily expose the subjects to the risk and whenever appropriate, by procedures already being performed on the subjects for diagnostic purpose?
  - N/A
  
2. Are the risk to the subjects reasonable in relation to
  - a) The benefits that might be reasonably be expected as an outcome to the subjects/others.
    - N/A
  
  - b) Provision for free treatment for research related injury.
    - N/A
  
  - c) Compensation of subjects for disability or death resulting from such injury
    - N/A
  
  - d) The importance of the knowledge that may reasonably be expected to result from the research project
    - N/A
  
3. Will informed consent be sought from each positive subject /legally authorised representative?
  - YES
  
4. Does the research plan make adequate provisions for confidentiality and monitoring the data collected to ensure the safety of subjects?
  - YES

## **Introduction**

Epidemiologic studies have found the Lewis negative phenotype to be independently associated with a two-fold higher prevalence of coronary artery disease and four-fold fatal coronary events . Lewis (a-b-) blood group has been reported to be associated with hypercholesterolemia, diabetes mellitus and insulin resistance conditions which eventually lead to CAD . Many studies have also shown the relationship between blood groups and different manifestations of cardiovascular disease .

Different clinical studies have shown that blood A phenotypes are more susceptible to coronary artery disease . The major one being the Framingham study .

In contrast, Garg P et al. reported a significant association between CAD and blood group B. while Sahita P et al. from Gujarat, India, did not observe any association between blood group and CAD. Cakir B et al reported a non- significant association between Lewis genotype and subclinical atherosclerosis and Saloma V et al. observed that carotid intima-media thickness was slightly higher among persons with Lewis negative phenotype than among persons with Lewis positive phenotype.

There is no literature from Kerala correlating Lewis antigen and ABO blood group with CAD, hence the present study to focus on the pattern and association of ABO and Lewis blood group phenotypes in clinically confirmed CAD patients.

## **Rationale**

The present study aims to evaluate the association between Lewis antigen, ABO blood group, and coronary artery disease. This may allow identifying subjects at increased risk for coronary artery disease (CAD) and subsequently leading to more focused preventive measures and eventually to a specific treatment.

## **Review of literature**

Coronary artery disease in Kerala is progressive and degenerative resulting in death at a very young age. The prevalence of definite CAD in Kerala increased nearly three times since 1993 without any difference in urban and rural areas. Most risk factors of CAD are highly prevalent in the state Hence early detection of these risk factors is highly essential to curtail CAD.

The ABO and Lewis blood group systems have both been linked to ischaemic heart disease (IHD) .

The Lewis Antigens play a well-defined role in selectin-mediated cell adhesion events, and in inflammation and defense against infection. In the absence of these antigens, as in Le(a-b-), inflammation and chronic infection, in turn contribute to the multifactorial pathogenesis of coronary disease events. Like the ABO blood group, the Lewis blood group reflects the actions of two distinct glycosyltransferases, FUT2/Secretor and Lewis/FUT3, an α1,3/4-fucosyltransferase.

T. Alexy et al. reported hypertriglyceridemia, insulin resistance, and higher prevalence of non-insulin dependent diabetes mellitus in the Le(a-b-) population . M.N.Hasan et al revealed a higher prevalence of CAD in patients with blood group B .

In a study conducted by Enevold et al, no significant associations were observed between Lewis blood group/AB0 blood groups and hypertension, IHD, or obesity . The meta-analysis by Zhuo Chen et al suggests that blood group A and non-O are associated with an increased risk of CAD . A study by Sharif S et al showed that subjects with blood group A had a significantly higher risk of developing IHD compared to other blood groups .

## **Materials and methods**

### **Research question:**

Does ABO and Lewis blood group phenotypes have an association with Coronary Artery Disease?

### **Aim and Objectives:**

#### **Primary objective**

- To study the association of Lewis antigen and ABO blood group phenotypes with CAD patients attending the tertiary care hospital in Kerala.

#### **Secondary objective**

- To find the association of Lewis antigen and ABO blood group phenotypes with smoking, alcohol use, diabetes, hypertension and dyslipidemia.

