## **Sampling:**

- Sample size**

Based on the proportion of Le(a-b-) observed in an earlier publication with 95% confidence level and 90% power, minimum sample size comes to 70 in cases and 140 in control group

$$n = \frac{[Z_{1-\alpha/2} \sqrt{2p(1-p)} + Z_{1-\beta} \sqrt{p_1(1-p_1) + p_2(1-p_2)}]^2}{(p_1 - p_2)^2}$$

- Inclusion criteria:**

- Patients in the age group of 30-55 years at the time of data collection
- Diagnosed with coronary artery disease on the basis of positive changes in coronary angiogram (More than 70% coronary stenosis)

- Exclusion Criteria:**

- Patients with other systemic illnesses like malignancy, autoimmune diseases.
- Patients who are not willing to participate in the study.

- Sampling procedure:**

First 70 cases attending the Cardiology department which satisfy the inclusion and exclusion criteria will be included in the study.

- Method of data collection**

70 cases attending the Cardiology department which satisfy the inclusion and exclusion criteria will be taken as cases. 140 age and gender matched healthy blood donors who are eligible to donate blood as per the inclusion and exclusion criteria of Drugs and Cosmetics Rules, 1945 are taken as controls.

After taking written, informed consent from the patients and blood donors satisfying the inclusion criteria, 3 mL blood is collected from cubital vein in Ethylene Diamine Tetra Acetic acid (EDTA) tubes under aseptic precautions. Samples are collected separately from each CAD patient as well as from blood donors.

Collection of blood samples repeatedly from the same subjects are avoided by personally verifying the subject's demographic profile such as full name, age, address, including hospital registration number and by collecting the blood sample in the required quantity.

Lipid profile values, fasting and post prandial blood sugar values will be collected from the laboratory information system. Blood pressure values will be obtained from the medical record and donor forms.

Diabetes mellitus is defined as fasting serum glucose  $>126$  mg/dL and or the reported use of diabetic medications. Hypertension is defined as systolic blood pressure (BP)  $>140$  or diastolic BP  $>90$  mmHg, or reported use of antihypertensive medications.

Alcohol use pattern is categorised as none, low/moderate use (1–14 drinks/week), and heavy use ( $>14$  drinks/week).

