## **Estimated expenditure**

Establishment

- Antisera : ₹ 50000/-
- Vacutainers : ₹ 1700/-

Equipment

: nil

Research literature

: ₹ 1000

Cost of preparation of research papers : ₹ 1000

Expenditure will be met by the institution.

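### Secondary objective only: the form records lipid values but not lipid treatment, so treated participants with normal values cannot be identified from it, and the smoking classes leave out current non-daily smokers

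*Combined protocol and SAP*

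**What the plan says.** The Secondary objective section states the aim as "To find the association of Lewis antigen and ABO blood group phenotypes with smoking, alcohol use, diabetes, hypertension and dyslipidemia". Method of data collection, under Sampling, then sets out four of these five variables.

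- Diabetes: a fasting glucose threshold and/or "the reported use of diabetic medications".
- Hypertension: a blood pressure threshold, "or reported use of antihypertensive medications".
- Alcohol: three bands of weekly intake.
- Smoking: three classes, built on 100 lifetime cigarettes and on whether the person now smokes daily or has quit.

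For the fifth variable, only a data source is given: "Lipid profile values, fasting and post prandial blood sugar values will be collected from the laboratory information system". No lipid fraction, cut-off or treatment rule follows.

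The Investigations part of the proforma repeats this pattern. Hypertension and diabetes each have a yes/no item and an on-medication item. The lipid block has total cholesterol, TG, HDL and LDL, with neither item. The first part of the proforma has an open line for past history, without a prompt for lipid treatment.

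Statistical analysis plans frequencies and a chi-square test on categorical data, so the four lipid values have to be turned into a category.

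**The concern.** The plan treats medication as evidence of disease for two of its three metabolic variables and does not ask about it for the third. If dyslipidemia is later defined by values alone, a participant treated to normal values counts as unaffected. If it is later defined to include medication, the form does not hold the information needed.

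The two gaps are not equally serious. Cut-offs can be applied after data collection, because the four values are kept in mg/dL. Treatment status that was not asked at enrolment may be lost.

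The smoking gap is a matter of logic. Someone who has smoked at least 100 cigarettes and now smokes on some days is excluded from all three classes. Without a stated rule, that person is assigned ad hoc or dropped.

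What is at stake is the interpretation of two of the five secondary variables. The primary comparison of phenotype with CAD uses neither, and no adjustment for risk factors is planned.

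**Working it through.** **1. The plan's own figure.** The only stated size is 70 cases and 140 controls, for the Le(a-b-) comparison. Nothing is stated for the secondary objective. The two proportions behind 70 and 140 are not given, so that figure can be neither reproduced nor refuted, and this point does not depend on it.

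**2. Items present for each metabolic variable.**

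| Variable | Definition | Medication counts | Medication item on form |
|---|---|---|---|
| Diabetes | yes | yes | yes |
| Hypertension | yes | yes | yes |
| Dyslipidemia | none | not stated | none |

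**3. Smoking classes, tested on a current non-daily smoker with at least 100 lifetime cigarettes.**

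- Smoker: fails, because daily smoking is required.
- Ex smoker: fails, because the person has not quit.
- Never smoker: fails, because 100 cigarettes have been reached.

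The number of such people cannot be derived from the documents.

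**4. Illustration of what an unrecorded treatment status can do.** Every input is assumed: cases only, a true odds ratio (OR) of 2.0 for dyslipidemia in Le(a-b-) versus other phenotypes, and a reference prevalence p0 of 0.30, 0.50 or 0.70.

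True prevalence in Le(a-b-): p1 = 2·odds(p0) / (1 + 2·odds(p0)), which gives 0.462, 0.667 and 0.824.

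- Values-only rule: a share m of dyslipidemic cases is normal on treatment and missed. Observed prevalence = p(1 − m).
- Values-or-medication rule: a share q of unaffected cases is treated because of CAD and counted. Observed prevalence = p + q(1 − p).

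Worked at p0 = 0.50 with a share of 0.30:

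- Values only: 0.667 × 0.7 = 0.467 and 0.50 × 0.7 = 0.350. OR = (0.467/0.533)/(0.350/0.650) = 1.625, shown below as 1.62.
- Values or medication: 0.667 + 0.3 × 0.333 = 0.767 and 0.50 + 0.3 × 0.50 = 0.650. OR = (0.767/0.233)/(0.650/0.350) = 1.77.

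Observed OR at error shares of 10%, 30% and 50%:

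| p0 | Values only (m) | Values or medication (q) |
|---|---|---|
| 0.30 | 1.92, 1.80, 1.70 | 1.81, 1.59, 1.46 |
| 0.50 | 1.83, 1.62, 1.50 | 1.91, 1.77, 1.67 |
| 0.70 | 1.68, 1.42, 1.30 | 1.96, 1.89, 1.82 |

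Both rules attenuate, and which one attenuates more depends on prevalence. The shares m and q are also different quantities, so a row compares the rules only if the two happen to be equal.

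**5. Power, on the same assumptions.** Take 40% of the 70 cases as Le(a-b-), that is 28 versus 42, with p0 = 0.50. Dyslipidemic cases number 28 × 0.667 + 42 × 0.50 = 39.7, and 30% of these is 11.9. Exact power of the uncorrected two-sided 5% chi-square test is 29% with perfect classification, 17% under values only with m = 30%, and 19% under values or medication with q = 30%.

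**6. Dependence on the independence assumption.** Steps 4 and 5 assume that the error share is the same in both phenotype groups. With equal shares, a true OR of 1.0 stays 1.0. With unequal shares it does not. At a true prevalence of 0.50 in both groups, missing 30% in Le(a-b-) and 10% in the others gives 0.35 versus 0.45, and OR = (0.35/0.65)/(0.45/0.55) = 0.66.

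**The case against.** **Recoverability.** The strongest objection is that little is lost for good. The lipid values are stored, so a cut-off can be set later. The form carries the hospital number, and the medical record is already a named source for blood pressure, so lipid treatment in cases might be looked up. This stands in part. It rules out saying that treatment status cannot be recovered, but no step in the plan requires the lookup.

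**Choice of rule.** A reader might infer that counting medication is the correct rule and that a values-only analysis is the flaw. The documents do not support that. The medication rule matches the plan's diabetes and hypertension definitions, but on the assumed inputs it attenuates more at 30% prevalence. At 50% prevalence it keeps little of the lost power (19% against 17%, from 29%). This objection stands in full and is the reason for reporting both rules.

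**Donor data.** A reader might also infer that "140 age and gender matched healthy blood donors" will have no lipid values. Donor forms are named only for blood pressure ("Blood pressure values will be obtained from the medical record and donor forms"), the study's own sample is described only for blood grouping and Lewis typing, and the expenditure list has no lipid assay. That is inference from silence. The laboratory-system sentence is not limited to cases, the proforma is headed for cases and controls alike, and the expenditure list has no glucose test either. The same doubt would apply to donor glucose, which comes from the same sentence. What remains is a question for the investigators.

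**Size.** Only a secondary objective is involved, and within-case power is low even with perfect classification. That stands. The gain is a variable with a known meaning, not recovered power.

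**Conclusion.** The point holds for the secondary objective, in two parts. First, the form as written cannot identify a participant whose lipids are normal on treatment, although the plan records and counts treatment for the two comparable variables. Second, the smoking classes have a gap. Both follow from the text and need no assumption.

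The size cannot be derived from the documents, which give no prevalence of dyslipidemia, no treatment rates and no phenotype shares. The illustration shows only that a true odds ratio of 2.0 could appear as anything from 1.30 to 1.96 over the assumed range, depending on rule, prevalence and error share. Attenuation towards 1 also rests on treatment being unrelated to phenotype. The Introduction and Review of literature report more lipid disturbance in Le(a-b-), so that cannot be presumed.

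The missing cut-offs alone are a lack of detail that can be repaired before analysis. The treatment item is the part to settle before data collection. A reader might infer that the phenotype-CAD result is compromised, but it is not: that comparison uses neither dyslipidemia nor smoking.

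**What to change.** 1. **Proforma, lipid block.** Add: *Lipid-lowering medication: yes / no; if yes, started before the CAD diagnosis (cases): yes / no.*
2. **Method of data collection.** Define dyslipidemia by named lipid fractions, with cut-offs chosen by the investigators and fixed before analysis. Report it in two ways: values or medication, in line with the diabetes and hypertension definitions, and values only.
3. **Smoking.** Widen the current-smoker class from daily smoking to smoking every day or some days.
4. **Note.** Confirm whether donor lipid and glucose values exist in the laboratory information system.

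The cost is one form line, one definition, a one-phrase edit and a second tabulation. No new test is asked for. The downside is that the medication rule will label some cases treated because of CAD as dyslipidemic; the start-before-diagnosis item and the values-only table would show how many.

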### **Study design**

Hospital-based case-control analytical study

### **Study setting and duration:**

The Study will be conducted over a period of eighteen months in the Department of Transfusion Medicine in association with Department of Cardiology at Jubilee Mission Medical College and Research Institute, Thrissur, a tertiary care multispecialty teaching hospital in central Kerala.

## **Sampling:**

- Sample size**

Based on the proportion of Le(a-b-) observed in an earlier publication with 95% confidence level and 90% power, minimum sample size comes to 70 in cases and 140 in control group

$$n = \frac{[Z_{1-\alpha/2} \sqrt{2p(1-p)} + Z_{1-\beta} \sqrt{p_1(1-p_1) + p_2(1-p_2)}]^2}{(p_1 - p_2)^2}$$

- Inclusion criteria:**

- Patients in the age group of 30-55 years at the time of data collection
- Diagnosed with coronary artery disease on the basis of positive changes in coronary angiogram (More than 70% coronary stenosis)

- Exclusion Criteria:**

- Patients with other systemic illnesses like malignancy, autoimmune diseases.
- Patients who are not willing to participate in the study.

- Sampling procedure:**

First 70 cases attending the Cardiology department which satisfy the inclusion and exclusion criteria will be included in the study.

- Method of data collection**

70 cases attending the Cardiology department which satisfy the inclusion and exclusion criteria will be taken as cases. 140 age and gender matched healthy blood donors who are eligible to donate blood as per the inclusion and exclusion criteria of Drugs and Cosmetics Rules, 1945 are taken as controls.

After taking written, informed consent from the patients and blood donors satisfying the inclusion criteria, 3 mL blood is collected from cubital vein in Ethylene Diamine Tetra Acetic acid (EDTA) tubes under aseptic precautions. Samples are collected separately from each CAD patient as well as from blood donors.

Collection of blood samples repeatedly from the same subjects are avoided by personally verifying the subject's demographic profile such as full name, age, address, including hospital registration number and by collecting the blood sample in the required quantity.

Lipid profile values, fasting and post prandial blood sugar values will be collected from the laboratory information system. Blood pressure values will be obtained from the medical record and donor forms.

Diabetes mellitus is defined as fasting serum glucose  $>126$  mg/dL and or the reported use of diabetic medications. Hypertension is defined as systolic blood pressure (BP)  $>140$  or diastolic BP  $>90$  mmHg, or reported use of antihypertensive medications.

Alcohol use pattern is categorised as none, low/moderate use (1–14 drinks/week), and heavy use ( $>14$  drinks/week).

Smoking pattern is categorised as Smoker (An adult who has smoked at least 100 cigarettes in his or her lifetime, and who now smokes every day), Ex smoker (An adult who has smoked at least 100 cigarettes in his or her lifetime but who had quit smoking), Never smoker: An adult who has never smoked, or who has smoked less than 100 cigarettes in his or her lifetime.

ABO blood grouping is performed according to department's Standard Operational Procedures (SOP). Commercially available monoclonal blood group antisera are used for forward grouping; for reverse grouping 5% pooled suspension of A, B and O cells are used which are prepared according to SOP.

Lewis antigen typing is done by using monoclonal antisera as per manufacturer's instructions.

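### Recent red-cell transfusion is neither excluded nor specifically recorded, so Lewis type, read once from circulating cells, may be misread in cases more often than in donors; the effect is probably small

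*Combined protocol and SAP*

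**What the plan says.** The Exclusion Criteria under Sampling in the combined protocol and SAP have two entries: "Patients with other systemic illnesses like malignancy, autoimmune diseases" and "Patients who are not willing to participate in the study". Cases are taken consecutively: "First 70 cases attending the Cardiology department which satisfy the inclusion and exclusion criteria will be included in the study". No rule links the time of sampling to an earlier admission, procedure or transfusion.

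Controls pass an additional screen. They are "140 age and gender matched healthy blood donors who are eligible to donate blood" under the cited national rules, whose content is not reproduced.

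On the specimen, Method of data collection says that "3 mL blood is collected from cubital vein in Ethylene Diamine Tetra Acetic acid (EDTA) tubes", and it aims to avoid sampling the same person twice. For Lewis, "Lewis antigen typing is done by using monoclonal antisera as per manufacturer's instructions"; no genotype, saliva test or repeat reading is mentioned. For ABO there are two readings: "Commercially available monoclonal blood group antisera are used for forward grouping; for reverse grouping 5% pooled suspension of A, B and O cells are used".

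The proforma has a free-text line for past history and a hospital number, but no transfusion field. The Statistical analysis section plans a chi-square comparison and says nothing about subjects whose typing may be unreliable.

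**The concern.** The primary objective relates Lewis and ABO phenotype to coronary artery disease, and the sample size is built on the proportion with Le(a-b-). That phenotype is meant to be a fixed characteristic of the subject, but it is measured on whatever red cells are circulating when the sample is drawn. If some of these came from a donor, the reading may not be the subject's own.

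The opportunity for this error differs between the groups. Cases come from a cardiology service with no limit on previous admission, bleeding or procedures. Controls must be healthy and fit to donate. The resulting misclassification would be differential. If most donor units are Lewis-positive, the typical error is a true Le(a-b-) case read as positive, which weakens a true positive association. The chi-square test cannot correct for this, and without a dedicated item the affected subjects would not be reliably identifiable at analysis.

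**Working it through.** **The plan's own figure.** The Sample size paragraph gives 70 cases and 140 controls at 95% confidence and 90% power. The two Le(a-b-) proportions come from an earlier publication and are not stated, so 70/140 can be neither confirmed nor refuted. I therefore solved backwards for pairs that give 70 cases at 1:2, with two-sided alpha 0.05, pooled variance and no continuity correction. The control proportions are assumptions.

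- Controls p2 = 0.10 require cases p1 = 0.282: odds ratio 3.53, power 90.1%.
- Controls p2 = 0.20 require cases p1 = 0.415: odds ratio 2.84, power 90.1%.

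The formula as printed is for equal groups. With 70 per group it requires larger p1, namely 0.320 and 0.454. Power at 70/140 would then start above 90%, so the pairs used here are not the favourable choice.

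**Error model.** Let f be the share of cases recently transfused (assumed; not in the documents). As an upper bound, every transfused Le(a-b-) case is read as Lewis-positive and no control is misread. The observed proportion in cases is q = p1 × (1 − f), and the expected number of misread cases is 70 × p1 × f.

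**Power formula.** Power = Φ[(q − p2 − 1.96·s0)/s1], where s0 = √[p̄(1 − p̄)(1/70 + 1/140)], s1 = √[q(1 − q)/70 + p2(1 − p2)/140] and p̄ = (70q + 140p2)/210.

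**Example, p2 = 0.10 and f = 5%.** q = 0.282 × 0.95 = 0.2679. p̄ = (70 × 0.2679 + 140 × 0.10)/210 = 0.1560. s0 = 0.0531 and s1 = 0.0587. Power = Φ[(0.1679 − 1.96 × 0.0531)/0.0587] = Φ(1.09), about 86%.

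| f | p2 = 0.10: misread cases; OR; power | p2 = 0.20: misread cases; OR; power |
|---|---|---|
| 0% | 0; 3.53; 90.1% | 0; 2.84; 90.1% |
| 2% | 0.4; 3.44; 88.7% | 0.6; 2.74; 88.0% |
| 5% | 1.0; 3.29; 86.1% | 1.5; 2.60; 84.2% |
| 10% | 2.0; 3.06; 81.1% | 2.9; 2.38; 76.3% |

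**A milder model.** If a mistyped case instead takes a type with the control distribution, q = (1 − f)p1 + f·p2, where f is now the share of cases mistyped. Power at f = 5% is 87.7% (p2 = 0.10) or 87.3% (p2 = 0.20).

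**No true association.** With the one-way error (Le(a-b-) read as positive) and f = 5%, the observed odds ratio is about 0.94 and the two-sided rejection rate is 5.0% (p2 = 0.10) or 5.2% (p2 = 0.20). This mechanism hardly creates false positives.

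**Recruitment cost of excluding.** Candidates needed to fill 70 case places are 70/(1 − f): 70/0.98 gives 72, 70/0.95 gives 74 and 70/0.90 gives 78.

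**The case against.** The strongest reply is that nothing in the documents shows that any case aged 30 to 55 with angiographic disease will have been recently transfused. Even under the worst-case error model, 2% transfused means fewer than one misread case in 70, and the odds ratio moves by about 0.1, which is trivial beside sampling error. The bias is also conservative. All of this stands, and it is why the point is a limited one.

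Three stronger readings are tempting but not supported.

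- **That ABO types will be wrong as well.** Reverse grouping tests the subject's own antibodies, and a mixed-field forward reaction is visible rather than silent. How the departmental procedure resolves a discrepancy is not shown, so wrong ABO results cannot be asserted.
- **That affected subjects could never be found.** The past-history line and hospital number might allow retrieval, and the plan already draws on medical records and the laboratory system. What is missing is a guarantee that transfusion is asked about and recorded.
- **That power would fall to about 55%.** That figure comes from assuming 30% against 15%, where 70/140 has only 71% power before any error, together with 10% of cases transfused and every transfused Le(a-b-) case misread. The plan states 90%, so that starting point is not its own.

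The low risk in donors and the direction of bias also rest on premises outside the text: the eligibility rules are cited but not reproduced, and no proportion of Lewis-positive donor units is given. If errors instead produced false Le(a-b-) readings in cases, the bias would run away from 1. Nothing in the documents points to that.

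**Conclusion.** The gap is real and limited. Followed as written, the plan would type and count a recently transfused case like any other, on a single Lewis reading with no cross-check, while controls face a health and eligibility screen that cases do not. The risk is differential misclassification, mainly of Lewis type, and probably toward the null where a true association exists.

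With effects consistent with the planned 90% power, the upper-bound loss is 1 to 2 percentage points of power at 2% transfused, 4 to 6 at 5% and 9 to 14 at 10%. These figures rest on assumed Le(a-b-) proportions, an assumed transfused share, mostly Lewis-positive donor units, and complete misreading of transfused Le(a-b-) cases. It is worth correcting because it touches the exposure behind the sample size, is hard to repair after sampling, and costs little to close.

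**What to change.** Add to the proforma, for cases and controls alike, a yes/no item for red-cell transfusion with the date of the latest one.

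Add an exclusion for subjects transfused within a pre-specified window before sampling. The transfusion department should set and justify the window; 3 months is one example, but the documents do not supply it. Replace each excluded subject by the next consecutive eligible one (for controls, keeping the age and gender matching) so that 70/140 is kept.

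If exclusion is not wanted, the minimum is a pre-specified sensitivity analysis that repeats the Lewis comparison without transfused subjects.

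The cost is one form item and one line of text, with no extra test. A few cases are passed over and recruitment is slightly longer: about 74 candidates to fill 70 places if 5% were transfused.

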## **Statistical analysis**

Statistical analysis will be carried out using SPSS version 25.0. Descriptive Statistics for the categorical variables are performed by computing the frequencies (percentages) in each category. Comparison of categorical data between association of ABO and Lewis phenotypes in clinically confirmed CAD patients is done using chi-square test.

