**Investigations**

Angiogram : \_\_\_\_\_

Hypertension:  yes  noOn medication:  yes  no

BP: \_\_\_\_\_ mmHg

Lipid profile:

Total Cholesterol : \_\_\_\_\_ mg/dL

TG : \_\_\_\_\_ mg/dL

HDL : \_\_\_\_\_ mg/dL

LDL : \_\_\_\_\_ mg/dL

Diabetes:  yes  noOn medication  yes  no

PPBS : \_\_\_\_\_ mg/dL

FBS : \_\_\_\_\_ mg/dL

Blood Group			
A	B	AB	O
+	-		

Rh	
+	-

Le a	
+	-

Le b	
+	-

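### Healthy, donor-eligible controls may under-represent Le(a-b-) and bias the Lewis-CAD odds ratio upward, and the chi-square-only analysis neither measures nor qualifies this

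*Combined protocol and SAP*

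**What the plan says.** In the protocol's Sampling section, under the method of data collection, controls are "140 age and gender matched healthy blood donors who are eligible to donate blood as per the inclusion and exclusion criteria" of a rule cited by name. That rule is not reproduced, and healthy is not defined.

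The case exclusions give malignancy and autoimmune disease as examples of systemic illness and do not name diabetes. Diabetes is defined in the same section and is recorded on the proforma, which serves cases and controls alike. It is also part of the secondary objective: "To find the association of Lewis antigen and ABO blood group phenotypes with smoking, alcohol use, diabetes, hypertension and dyslipidemia". Cases with diabetes are therefore evidently kept.

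The protocol ties the exposure to diabetes twice. The Introduction states: "Lewis (a-b-) blood group has been reported to be associated with hypercholesterolemia, diabetes mellitus and insulin resistance conditions which eventually lead to CAD". The Review of literature reports a "higher prevalence of non-insulin dependent diabetes mellitus in the Le(a-b-) population".

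Beyond frequencies and percentages, the Statistical analysis section plans one procedure: "Comparison of categorical data between association of ABO and Lewis phenotypes in clinically confirmed CAD patients is done using chi-square test". It has no odds ratio, confidence interval, adjustment, restriction or sensitivity analysis.

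**The concern.** A case-control OR is interpretable when controls show the exposure frequency of the population that produced the cases. Here a health filter applies to controls and not to cases, and it may act on a condition that the protocol says is commoner in Le(a-b-) people. If so, Le(a-b-) people are removed preferentially from the control side, and whatever the true OR is, it is multiplied upward.

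The secondary Lewis-by-diabetes comparison bears on the premise, but it does not show what control selection does to the Lewis-CAD comparison. A bare chi-square result gives no effect size that a reader could discount. The Rationale hopes to identify people at increased risk, so the size of the association and the nature of the comparator both matter.

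**Working it through.** **The plan's own figure.** The Sampling section states that the "minimum sample size comes to 70 in cases and 140 in control group", at 95% confidence and 90% power. The two Le(a-b-) proportions are not given, so this can be neither reproduced nor refuted. Solving backwards at 1:2 allocation, 70 cases fit, for example, 20.3% vs 5% (OR 4.8), 41.5% vs 20% (OR 2.8) or 53% vs 30% (OR 2.6). The study is therefore sized for an OR of about 2.6-4.8 at assumed control frequencies of 30% down to 5%.

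**Bias factor.** Let q be the Le(a-b-) frequency in the source population, c1 and c0 the diabetes prevalence in Le(a-b-) and Lewis-positive people, and d the share of diabetic donors deferred. The documents give none of these, so all are assumed.

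- Source odds of Le(a-b-): q/(1 − q).
- Odds among selected controls: q(1 − d·c1) / [(1 − q)(1 − d·c0)].
- Factor on the OR: (1 − d·c0)/(1 − d·c1), which does not depend on q.

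| c0 | c1 | d = 1 | d = 0.5 | d = 0 |
|---|---|---|---|---|
| 0.10 | 0.15 | 0.90/0.85 = 1.06 | 0.95/0.925 = 1.03 | 1.00 |
| 0.10 | 0.20 | 0.90/0.80 = 1.13 | 0.95/0.90 = 1.06 | 1.00 |
| 0.20 | 0.30 | 0.80/0.70 = 1.14 | 0.90/0.85 = 1.06 | 1.00 |
| 0.20 | 0.40 | 0.80/0.60 = 1.33 | 0.90/0.80 = 1.13 | 1.00 |

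A second parameterisation fixes overall diabetes prevalence and a Lewis-diabetes OR. At full deferral it gives about 1.05 (10%, OR 1.5), 1.18-1.19 (20%, OR 2) and up to 1.50-1.55 (30%, OR 3). With no Lewis-diabetes association the factor is exactly 1.00.

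**Effect on the test when the true OR is 1.** By normal approximation at 70 vs 140 with full deferral, the 5% type I error becomes about 5.3% (diabetes 10%, Lewis-diabetes OR 1.5, Le(a-b-) 10%), 7.6% (20%, OR 2, Le(a-b-) 20%) or 10% (30%, OR 2, Le(a-b-) 20%).

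**Effect on a result of the design size.** Suppose 29/70 vs 28/140. The OR is (29 × 112)/(41 × 28) = 2.83, 95% CI 1.51-5.31. Divided by 1.33 it is 2.12 (1.13-3.99). Divided by the extreme 1.55 it is 1.83 (0.97-3.43).

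**Controls with diabetes to expect, at q = 0.20.** The count is 140(1 − d)[q·c1 + (1 − q)c0] / [q(1 − d·c1) + (1 − q)(1 − d·c0)].

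- No deferral: from 140 × 0.11 = 15.4 to 140 × 0.24 = 33.6.
- Half deferral: 8.1 to 19.1.
- Full deferral: 0.

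The first two ranges overlap.

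**Restricting cases alone.** With no true association this gives an OR of [(1 − c1)/(1 − c0)] / [(1 − d·c1)/(1 − d·c0)]: 0.75-0.94 at no deferral, 0.84-0.97 at half and 1.00 at full. Unless deferral is complete, it swaps an upward bias for a downward one.

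**Precision after restricting both groups.** Assume 35-45 cases remain. At most about 34 controls are lost, so 106-140 remain. By the pooled-variance formula, power for 41.5% vs 20% is 0.70 (35/106) to 0.80 (45/140), against 0.90 at 70/140. With c0 = 0.20 and c1 = 0.40, Le(a-b-) among non-diabetic people is 0.2 × 0.6/(0.2 × 0.6 + 0.8 × 0.8) = 15.8%. The standard error of the log OR is √{[1/n1 + 1/n2]/[0.158 × 0.842]}: 0.534 at 35/106 and 0.484 at 45/112. The 95% limits around a null OR are then 0.35-2.9 and 0.39-2.6.

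**The case against.** The strongest objection is that the mechanism depends on a rule the reader cannot see. The donor regulations are named but not reproduced, and one form records diabetes and medication for both groups, so the documents do not show that diabetic donors are absent. That stands: the bias is conditional, and its range includes none at all. The undefined health requirement is a second possible filter, but it does not settle the matter either.

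It also stands that every magnitude is assumed. The 1.33 needs 40% diabetes among Le(a-b-) people aged 30-55 and complete deferral. Equally free assumptions reach 1.55.

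Donor controls are a common and deliberate choice, and nothing here requires replacing them. Diabetes status is already collected, so a restricted analysis would be possible without a protocol change. Pre-specification still protects against choosing it after seeing the result.

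The supportive analysis cannot decide the question: its limits are too wide, and diabetes may lie on a real pathway from Lewis phenotype to CAD. It also addresses diabetes only, while the protocol links Le(a-b-) to hypercholesterolemia and insulin resistance as well. These limits stand and should be stated with the result.

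A reader might infer that diabetic donors are certainly excluded, that a positive finding would be an artefact, or that the restricted OR is the corrected one. The documents support none of these. They do not state the deferral practice, the factor is small beside the ORs the study is sized for, and the restricted OR answers a different question.

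**Conclusion.** The concern holds in conditional form. The upward direction follows from the protocol's own statements wherever diabetic donors are screened out. Under the main assumptions the size is modest, a factor of 1.00-1.33, with about 1.55 at the extreme. It would not by itself produce an OR of 2.6-4.8. The illustrative design-size result keeps a lower limit above 1 after division by 1.33, though not by 1.55. The practical risk is a small or borderline association read as a population effect, with no estimate or caveat to temper it. This is an inexpensive improvement to consider, not a flaw that invalidates the design.

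**What to change.** 1. In the Statistical analysis section, report the Le(a-b-) case-control OR with 95% CI, adjusted for age and sex, alongside the chi-square test.
2. Report how many controls have diabetes, using the form's diabetes and medication items for both groups. The protocol says "Lipid profile values, fasting and post prandial blood sugar values will be collected from the laboratory information system", and donors may have no values there, which would make a laboratory-based count misleadingly low. Treat a low count as consistent with selection, not as proof of it.
3. Pre-specify one supportive analysis restricting both cases and controls, never cases alone, to people without diabetes. Restriction breaks the age and gender matching, so use the same age and sex adjustment as in the main OR. The two estimates then differ only in the restriction.
4. Word the conclusion as an association relative to healthy blood donors. State that a difference between the two ORs may reflect control selection, a real pathway through diabetes, or chance, and that selection on other conditions such as dyslipidemia or hypertension is not removed.

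The cost is one logistic model fitted twice, one count and some wording. No new participants, samples or form fields are needed. The downside is imprecision: with power of about 70-80% for 41.5% vs 20%, and null limits of roughly 0.35-2.9 to 0.39-2.6, the restricted OR can neither confirm nor exclude a shift of 1.1-1.3 and must be labelled supportive.
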